Evaluating Technology Enabled Services in Perinatal Depression

NCT05525689

11.2.23

STU#:00211815

PROTOCOL TITLE: Technology-Enabled Services to Support Care Managers in Obstetrics Clinics to Treat Perinatal Depression

SHORT TITLE: Evaluating Technology Enabled Services in COMPASS

PRINCIPAL INVESTIGATORS:

[name], MPH
 Division Director of Maternal-Fetal Medicine
 Women and Infants Hospital
 Associate Professor, Department of Obstetrics and Gynecology
 Warren Alpert Medical School of Brown University
 Women and Infants Health, Care New England
 [name]

[name]
 Feinberg School of Medicine
 Department of Preventive Medicine
 [contact]
 [contact]

VERSION DATE: 10.18.2023

STUDY SUMMARY:

Investigational Agent(s) (Drugs or Devices)	
IND / IDE / HDE #	
Indicate Special Population(s)	 Children  Children who are wards of the state  Adults Unable to Consent  Cognitively Impaired Adults  Neonates of Uncertain Viability  Pregnant Women  Prisoners (or other detained/paroled individuals)  Students/Employees
Sample Size	85
Funding Source	National Institutes of Health
Indicate the type of consent to be obtained	 Written  Verbal/Waiver of Documentation of Informed Consent  Waiver of HIPAA Authorization  Waiver/Alteration of Consent Process
Site	 Lead Site (For A Multiple Site Research Study)  Data Coordinating Center (DCC)
Research Related Radiation Exposure	 Yes  No
DSMB / DMC / IDMC	 Yes  No

OBJECTIVES

The aim of this study is to test a Technology Enabled Service (TES) to support the treatment of depression in the context of a collaborative care service (called COMPASS) in the Northwestern Medical

STU#:00211815

obstetrics clinics. The TES consists of digital technologies that connect patients to Care Managers remotely, providing tools for monitoring patient symptoms, communication, and delivery of a digital intervention.

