TESs can (a) include dashboards/interfaces to automate Care Manager (CM) tasks and streamline CM workflows for population-based case review; (b) connect the CM to both patients and providers, facilitating communication about stepped care among the entire care team; and (c) directly deliver digital treatments to people who are unable to engage in person due to logistical barriers common in the Perinatal period. Smartphones are broadly available among reproductive aged people and are owned by 94% of Americans under age 30 and 89% ages 31-49.²⁷⁻²⁹ Several RCTs have shown that digital interventions delivered through smartphones are effective in reducing Postpartum Depression.³⁰ As such, a TES can integrate a seamless service in which adherence to the core tenets of CC are facilitated by

STU#:00211815

digital technologies, but this novel application of TES has not been previously studied.

STUDY ENDPOINTS

We will utilize a pragmatic, RCT based on our OEI hybrid trial design.⁵³⁻⁵⁵ A total of 85 people (75 from Northwestern and 10 from Women and Infants Hospital) will be randomized to either TES or enhanced treatment as usual (eTAU). Descriptions of the TES and eTAU interventions appear in the next section labeled “Study Intervention(s)/ Investigational Agent(s).” Depressive symptoms and other outcomes will be measured at baseline and at 6 and 12 weeks. Beyond 12 weeks, participants will be allowed to continue use of the TES app and the eTAU website for the duration of the grant-funded budget period. App and website use will be tracked for the entire study duration.

STUDY INTERVENTION(S) / INVESTIGATIONAL AGENT(S)

Participants will be assigned to receive one of two study interventions: (1) a Technology Enabled Service, or (2) Enhanced Treatment as Usual. The design of the TES and eTAU interventions were determined through the design study (STU# STU00211314) and negotiations with our software development contractor (Adaptive Health).

Technology-Enabled Service (TES)

The TES will be based on Adaptive Health’s IntelliCare platform (described below). The TES will permit use of text message communication. Text message content will meet HIPAA standards, and will not contain information that might identify the patient as being in treatment for depression. Text message communication may be used to encourage IntelliCare app use or arrange phone calls to avoid risk of loss of confidentiality.

IntelliCare

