The IntelliCare intervention consists of 2 components: (1) a patient-facing app for assessment and self-management of depression, (2) a Care Manager dashboard. A brief description of each component appears below:

1. Patient-facing app: The patient-facing app contains the following tools for the assessment and self-management of depression:
 - Assessment: Within the IntelliCare App, participants will be prompted to complete an assessment of current (within the prior 2 weeks) depressive and anxiety symptoms.
 - Self-management: IntelliCare depression and anxiety self-management modules will be used in the trial. Each module represents a single behavioral strategy (e.g., scheduling positive behaviors, thought restructuring, goal setting), and takes only a few seconds to use. The modules address specific treatment goals, and may include instructional content as well as interactional components (e.g., activity scheduling/monitoring, thought records) that support behavior change. All participants will download the main app onto their own phones and will be encouraged to use the modules as directed by the CM throughout the study period.
2. Care Manager Dashboard: The CM dashboard displays which modules are being used by which patients, supporting efficient triage and clinical decision making. The dashboard also includes mental health assessment scores, a place to document notes about patient interactions, and a text messaging interface.

Enhanced Treatment as Usual (eTAU)

The eTAU will consist of current care plus access to a website (compass-care.northwestern.edu) that will provide content specific to perinatal depression. Patients randomized to eTAU will communicate with their Care Managers using phone or MyChart, which is consistent with standard clinical practice.

PROCEDURES INVOLVED

This is a multi-pronged prospective investigation of a TES to improve collaborative care service delivery to people with perinatal depression. Participants will be enrolled in a pragmatic RCT with outcome assessments at baseline, 6 and 12 weeks.

Data will be gathered from study participants as outlined in the table below. We have described how data collection methods differ by randomization assignment where applicable.

STU#:00211815

Table 1. Effectiveness Measures

Outcome/Construct	Measure Name	Method	Timing

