been bothered by thoughts that you would be better off dead or of hurting yourself in some way") a 1 or higher, a second suicidality question from the Beck Depression Inventory (BDI) is administered that is more specific in identifying suicide risk. Participants who indicate that they would like to kill themselves, or would kill themselves are considered "at risk." All CMs are notified via an alert in the TES and/or by the research team directly via email within one business day. The first CM to receive the notification will call the patient for a risk assessment based on the Columbia-Suicide Severity Rating Scale by phone within one business day. If an acknowledgement is not made by a CM, a member from the research team or clinical supervisor will follow up with the CM. Once acknowledgement is made by the CM, the Columbia-Suicide Severity Rating Scale is conducted as a routine part of clinical care. For patients who are at greater than low risk, the CM takes all necessary actions to ensure the safety of the patient, including considering the use of psychiatric hospitalization. If the patient does not respond to contact attempts from the CM, the patient's medical emergency contact, on file for all COMPASS patients, is called to assist in contacting the patient. In the rare event that contact cannot be made, CM's may contact emergency services for a wellness check in accordance with COMPASS procedures. When suicidality is expressed by the patient directly to the CM, the CM similarly follows up to conduct an evaluation and perform safety procedures. Perinatal psychiatrists are available for consultation with CMs and for follow-up consultation with any patient perceived to be at risk. For patients who are not at immediate risk and who do not require hospitalization, an outpatient psychiatric evaluation may be coordinated by the CM. A member from the research team or the clinical supervisor will follow up if the CM does not within two business days.

We note that these are risks inherent in the population and would occur whether or not they were enrolled in the study. We do not believe that the risk of these depressive, suicidal, or other adverse outcomes are increased as a function of being enrolled in this study or receiving TES during the trial phases. All potential risks associated with participation in this study are disclosed in consent documents.

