The PIs, with the support of the entire research team, will follow procedures outlined under the "Protection of Human Subjects" document that will serve as part of the quality control process for data confidentiality. The PIs will engage with the study team and case managers on a regular basis to ensure data accuracy and protocol adherence.

To ensure the validity and integrity of study data, the PIs, assisted by the Center statistical team, will oversee data management and data checking. Study data are accessible at all times for the PIs, the biostatistician, and all relevant Co-Is to review. The biostatistical team and study manager will conduct

STU#:00211815

analyses of accrual, drop-outs, protocol deviations on a monthly basis initially, which may drop to quarterly once we are confident that procedures are functioning adequately.

[name] will review adverse events (AEs) and serious adverse events (SAEs) individually in real-time and in aggregate at each DSMB meeting (not less than annually). They will review the information and make judgments on whether the events were study-related and the severity of the adverse event. These events will be recorded on an Adverse Event Form. Depending on the consensus of the review, further action will be taken to revise the intervention to avoid future events or the study will be stopped if significant harm is anticipated. The PIs ensure all protocol deviations, AEs, and SAEs are reported to the IRB and the NIMH program officer according to the applicable regulatory requirements.

For this study, the following standard AE definitions are used:

Adverse event: Any unfavorable and unintended sign or symptom temporally associated with the use of digital mental health interventions, regardless of whether it is considered related to intervention.

Serious Adverse Event: Any AE that results in any of the following outcomes:

- Death
- Life-threatening situation
- Event requiring inpatient hospitalization or prolongation of existing hospitalization
- Persistent or significant disability/incapacity

AEs are graded according to the following scale:

- Mild: An experience that is transient, and requires no special treatment or intervention. The experience does not generally interfere with usual daily activities.
- Moderate: An experience that is alleviated with simple therapeutic treatments. The experience impacts usual daily activities.

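### The AE and SAE definitions depend on use of an undefined class of digital interventions, so events in eTAU participants and in TES non-users may not qualify

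*Protocol*

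**What the plan says.** The Protocol, under Provisions to Monitor the Data to Ensure the Safety of Participants, defines an adverse event as an untoward sign or symptom "temporally associated with the use of digital mental health interventions", whether or not it is judged to be related to the intervention. A serious adverse event is "Any AE that results in any of the following outcomes", followed by the usual list: death, a life-threatening situation, inpatient or prolonged hospitalisation, and lasting disability.

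The attribution scale in the same section does not refer to digital interventions. It grades each event by its relation to study procedures. SAEs and certain treatment-associated AEs must reach the IRB and the NIMH program officer within 24 hours. AEs and SAEs are reviewed one by one and in aggregate at DSMB meetings, and the review can lead to a change in the intervention or to stopping the study.

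The protocol does not say what counts as a digital mental health intervention. The Objectives describe the TES as "providing tools for monitoring patient symptoms, communication, and delivery of a digital intervention". The section on study interventions says "Participants will be assigned to receive one of two study interventions", and of the control arm, "The eTAU will consist of current care plus access to a website" with content on perinatal depression.

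The SAP covers effectiveness, moderation and power. It contains no safety analysis.

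**The concern.** In a randomised trial the safety definition should depend on being in the trial, not on what a participant does after randomisation. Here an event must first be linked in time to use of something that the protocol does not define, and that the two arms receive in different forms. Relatedness is then judged against a different and wider reference.

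Two things are at stake. The first is reporting: a serious event that is not an AE as written is not an SAE either, and so does not trigger the 24-hour rule. The second is comparability: if the definition admits events more readily in one arm, aggregate counts put before the DSMB cannot safely be read by arm.

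**Working it through.** No figure in the plan can be reproduced here, so the check is mainly a reading of the text, with one short calculation to show what the size would depend on.

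**Step 1, nesting.** The SAE definition starts from an AE. Any event excluded from the AE definition is therefore excluded from the SAE definition, however serious its outcome.

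**Step 2, the two readings of the undefined term.**

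| Reading | eTAU participants | TES participants |
|---|---|---|
| The term means the TES only | No event qualifies | Events in app users qualify; events in non-users may not |
| The website also counts | Events in website users qualify; events in non-users may not | Events in app users qualify; events in non-users may not |

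The documents do not settle which reading is meant. On both, some events can fall outside.

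**Step 3, whether use is likely to differ by arm.** All TES participants download the app and are encouraged to use its modules as the Care Manager directs, and text messages may prompt use (Study Intervention(s)). eTAU participants are given access to a website. App activity is logged under an individual ID. Website use is tracked by an analytics tool or plugin, and individual accounts are only a possibility (Data Management and Confidentiality). Use may therefore differ, and for some eTAU participants it may not be known. No usage rate is given for either arm.

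**Step 4, what the size would depend on.** Expected recorded events in an arm = n × r × u, where n is arm size, r the true event rate and u the proportion using the intervention. This treats events as independent of use. The values below are assumptions: 43 TES and 42 eTAU (a near-equal split of the protocol's 85; the SAP's power paragraph instead uses 45 and 30) and r = 10% in both arms.

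- Full TES use, half of eTAU: 43 × 0.10 × 1 = 4.3 against 42 × 0.10 × 0.5 = 2.1.
- 80% TES use, half of eTAU: 43 × 0.10 × 0.8 = 3.4 against 2.1.
- Half in both arms: 43 × 0.10 × 0.5 = 2.15 against 2.1.
- TES-only reading, full TES use: 4.3 against 0.

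The result runs from no imbalance to no recorded eTAU events at all, and if TES use were the lower of the two the direction would reverse. These lines show dependence on u; they do not estimate anything.

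**Step 5, two concrete paths.** Under Withdrawal of Participants, a psychiatric hospitalisation ends study participation. If this happens to an eTAU participant who never opened the website, the reason for leaving is documented, but the hospitalisation is not an SAE as defined. Separately, a TES participant who has a pregnancy loss is asked to stop using the app while follow-up is permitted. Later events in that participant may no longer be linked in time to use.

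**The case against.** The best defence is that the phrase is plural and broad, that eTAU is one of the two named study interventions, and that its depression website can reasonably be called a digital mental health intervention. On that view the definition reaches both arms, and what it excludes follows use rather than assignment. This stands, and it is why unequal capture can be called possible but not established.

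Several routes also make serious events visible in both arms. All participants receive automated self-report assessments, and a positive PHQ-9 item 9 leads to a further suicidality question. Alerts can go by research-team email as well as through the TES. Medical records are collected continuously without restriction by arm. Psychiatric hospitalisation ends participation in either arm. The safety section provides for regular review of all data and adverse events. A reader might infer that serious eTAU events would go unnoticed; these provisions do not support that. They help to detect events, but they do not change which events qualify as AEs or SAEs, so the gap in the definition remains. Staff may also record every event in practice and read the temporal link loosely, but the text does not require it.

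A reader might also infer that the protocol's stated view on harm is undermined. The protocol does not believe that such risks "are increased as a function of being enrolled in this study or receiving TES during the trial phases". That is a prospective statement resting on risks inherent in the population, not on trial counts. Moreover, under-capture in eTAU alone would make the TES look worse, not safer. Neither document specifies a between-arm comparison of adverse events.

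**Conclusion.** The point holds as a defect in the definition. Followed as written, the AE and SAE definitions can leave out events in eTAU participants (all of them if the term means the TES, website non-users if the website counts) and events in TES participants who do not use the app. Serious events among these may miss the 24-hour reporting rule, and capture may differ by arm.

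The stronger reading, that the definition by itself makes safety capture unequal by arm, is not supported: it needs either the narrow meaning of the term or different use in the two arms, and the documents establish neither. Without usage rates or an expected event rate, the size of any imbalance cannot be stated. The conclusion rests on taking the definition literally; it makes no claim about how staff record events in practice. It should be corrected, because the rule as written can give a wrong classification for a death or a hospitalisation and the correction is short.

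**What to change.** Keep the existing description of an untoward sign or symptom, but replace the condition on use with a time window: from randomisation through the end of study participation, in either arm, regardless of intervention use or relatedness. State that an event which itself ends participation, such as a hospitalisation, falls inside the window.

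The Study Endpoints section lets participants go on using the app or website beyond week 12. A plain week-12 cut-off would lose later events that the present wording includes. Retain, therefore, events temporally linked to that continued use, and show them separately, since they still depend on use.

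Leave the SAE as a subset of the revised AE. Use study procedures as the reference for relatedness in both the definition and the attribution scale. Tabulate AEs and SAEs by randomised arm for the DSMB.

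The cost is a short protocol edit, some additional events to record among eTAU participants and TES non-users, and one simple table.

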Evaluating Technology Enabled Services in Perinatal Depression

NCT05525689

04.15.24

Data Analysis Plan

Effectiveness. Effectiveness analyses will use intention to treat methods. Given potential bias due to the time delay of implementation, a comparison of population characteristics (race and ethnicity, age, gender, health status, mobile phone competence, baseline depression and other mental health treatments) must be made between patients receiving TES and the eTAU. Should the populations be different, propensity scores will be estimated for the likelihood of receiving TES, and models will adjust for those scores (trimming the data as necessary). After the population comparison and appropriate adjustment, we will compare overall effectiveness, using generalized linear mixed models (GLMM) to determine if there are differences in effectiveness between individuals receiving TES and eTAU over time, while accounting for intraclass correlations (ICC) within CMs, and clinics where necessary. Missing data will be managed through multiple imputation. Additional covariates will also be included to identify any substantive changes in the service, technologies, and/or implementation plan as a result of optimization.

Moderation of TES on effectiveness. We will examine any moderation of the effect of treatment arm on depressive symptoms by race, ethnicity, age, health status, substance/alcohol use, mobile phone competence, or other mental health treatments, in individual GLM models, by estimating a treatment by moderator interaction in predicting end of treatment depression scores adjusting for baseline levels of depression.

Power. Although a pilot study, we provide an estimate of effect that we can detect with a conservative recruitment of 30 participants in eTAU and 45 participants in TES. As power calculations for delayed roll-out trials involve both between period and within period autocorrelations, which would be speculative at this point, we estimated an effect size with an estimated ICC of 0.01 within clinics. With this assumption, we have 80% power to detect an effect size of 0.76 – a difference in PHQ-9 scores between eTAU and TES of 3.8 assuming a SD of 5. Given this trial is embedded in the COMPASS CC program that receives 30-50 referrals per month, we expect this trial will be able to enroll more participants than this conservative estimate, and as this is the calculated effect size for a simpler analysis, we anticipate this to be conservative estimate.

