We will compare the TES to an eTreatment As Usual (eTAU) consisting of current care plus access to a website [<http://compass-care.northwestern.edu/>] that will provide content specific to perinatal depression.

We will utilize a randomized clinical trial (RCT) to compare a technology enabled service (TES) intervention to enhanced treatment as usual (eTAU) within antenatal and postpartum women. Randomization will occur at the patient level. It is not feasible to mask participants or providers.

The primary effectiveness outcome is depression severity. Secondary outcomes are anxiety, and satisfaction with care.

Aims

Aim 1: Conduct a pilot Optimization-Effectiveness-Implementation (OEI) hybrid trial of a Technology Enabled Service (TES) for the treatment of depression compared to enhanced treatment as usual (eTAU).

Aim 2: Experimental therapeutics aims. Analyses will explore the mediating effects of the CM dashboard features that support the CM's treatment activities and workflow, including tracking symptom response, managing the stepped care processes, and communicating care plans. We will also explore the moderating effects of race, ethnicity, income, age, anxiety symptom severity, and mobile phone competence on the depression outcome.

BACKGROUND

Note: The "Background" section has been significantly reduced to create a more succinct protocol document. The original grant submission with the full background information is available upon request.

1. Perinatal depression is common and associated with adverse maternal and child outcomes.¹⁻⁵

Glossary of Terms:

- a. **Perinatal:** relating to the time, usually a number of weeks, immediately before and after birth.
 - a. **Antenatal:** before birth; prenatal.
 - b. **Postpartum:** The period just after delivery, as with postpartum depression. Postpartum refers to the mother, and postnatal to the baby.

2. Myriad barriers to effective treatment exist.⁶⁻¹¹

3. Collaborative Care (CC) represents an innovative health systems approach to depression treatment.¹²⁻²⁰

4. Perinatal Depression poses unique care challenges.²¹⁻²²

5. Significant gaps exist in Perinatal CC implementation.²³⁻²⁶

6. Technology enabled services (TES) may offer a solution for effective Perinatal CC delivery.

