Exclusion Criteria: Has experienced a pregnancy loss (miscarriage, termination, or stillbirth of the index pregnancy)*, has severe suicidality (as defined by the presence of a plan and intent to act on that plan), not parenting their child (i.e. adoption, foster care, etc.), anyone not meeting the inclusion criteria described above

*If a participant experiences a pregnancy loss during the trial, they will remain in the COMPASS program but they will be asked to stop using the app.

VULNERABLE POPULATIONS

This research will not impact the course of the pregnancy or health of the fetus. Our interview questions and assessments will not ask about the health or viability of the fetus, nor about decisions the client must make related to the health or viability of the fetus.

RECRUITMENT METHODS

Recruitment for the clinical trial will occur outside the context of usual Care Manager (CM) activities and once a participant is randomized, it will be fit into normal processes of care, to make the results as generalizable as possible. Patients may be identified a) during regular CM visits or b) through rosters pulled using Electronic Medical Records. All patients judged as being either pregnant or within 3 months of delivery who are at least 18 years of age will be given an electronic or verbal description of the study by the Care Manager or research team and screened for eligibility. Some patients may be given a flier/sent an email/sent a MyChart message with more information about the study before initiating the verbal screening procedure. CMs and the research team will record the results of all recruitment contacts.

All recruitment advertising materials have been uploaded to the eIRB+ system for review.

COMPENSATION FOR PARTICIPATION IN RESEARCH ACTIVITIES

We will reimburse all trial participants for completing research assessments.

STU#:00211815

All subjects can earn up to \$100 for completing online study assessments. Reimbursement for each completed assessment is outlined in table 3 below.

Table 3. Compensation for Completion of Online Surveys (All Participants)

Method	Week 0	Week 6	Week 12	Total
Self-report Survey	\$20	\$30	\$50	\$100

Week 0 will be paid after randomization and welcome call. Week 6 and week 12 will be paid upon survey completion.

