Effectiveness analyses will use intention to treat methods. To compare overall effectiveness, generalized linear mixed models (GLMM) will be used to determine if there are differences in effectiveness between individuals receiving TES and eTAU over time. Missing data will be examined for potential non-ignorable mechanisms, and will be managed through multiple imputation. Additional covariates will also be included to identify any substantive changes in the service, technologies, and/or implementation plan as a result of optimization. We will examine moderation of treatment arm by strata (postpartum or antenatal), and present results within each strata.

Moderation of TES on effectiveness. We will examine any moderation of the effect of treatment arm on depressive symptoms by race, ethnicity, age, health status, substance/alcohol use, mobile phone competence, or other mental health treatments, in individual GLM models, by estimating a treatment by moderator interaction in predicting end of treatment depression scores adjusting for baseline levels of depression.

Power. Although a pilot study, we provide an estimate of effect that we can detect with 100 randomized participants, as well as within strata of 80 and 20. As power calculations for repeated measures involve correlations over time which are speculative at this point, we provide effect size estimates for 12 month PHQ-9 scores based on an independent t-test. We have 80% power to detect an effect size of 0.58 for the entire cohort – a difference in PHQ-9 scores between eTAU and TES of 2.9 assuming a SD of 5; and effect sizes of 1.41 and 0.65 in antenatal and postpartum populations, which correspond to differences of 7.03 and 3.26 on the PHQ-9).

PROVISIONS TO MONITOR THE DATA TO ENSURE THE SAFETY OF PARTICIPANTS

Data and safety monitoring of participants will be monitored by the Principal Investigator, [name], who have primary responsibility for monitoring and will do so on a weekly basis during their planned meetings. [name] will regularly review all data and adverse events and will report all serious adverse events to the Northwestern University Institutional Review Board Requirements. Second, any reporting of significant mental or physical health-related symptoms by the participant to the study team will result in appropriate referrals to the participant's clinician or other appropriate facilities.

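### The SAP plans for a delayed roll-out that the protocol's patient-level RCT does not describe: observed group differences trigger propensity adjustment and optional trimming, with no stated rule

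*SAP*

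**What the plan says.** **Protocol (version 10.18.2023).** The Objectives section describes a randomised trial of TES against eTAU: "Randomization will occur at the patient level". Later sections agree. Study Endpoints gives the number to be randomised, "A total of 85 people (75 from Northwestern and 10 from Women and Infants Hospital"; the eTAU description says "Patients randomized to eTAU will communicate with their Care Managers using phone or MyChart"; Recruitment Methods says "once a participant is randomized, it will be fit into normal processes of care". The Data Analysis Plan specifies intention to treat, a generalised linear mixed model (GLMM) and multiple imputation. It has no time delay, propensity score or trimming.

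**SAP (04.15.24).** The Effectiveness paragraph opens with "Effectiveness analyses will use intention to treat methods". It continues: "Given potential bias due to the time delay of implementation, a comparison of population characteristics" must be made between patients receiving TES and eTAU. It lists race and ethnicity, age, gender, health status, mobile phone competence, baseline depression and other mental health treatments. If the groups differ, "propensity scores will be estimated for the likelihood of receiving TES, and models will adjust for those scores (trimming the data as necessary". The Power paragraph also refers to delayed roll-out trials. The SAP does not mention randomisation, does not define a difference, and gives no trimming rule.

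**The concern.** The SAP's procedure suits a comparison in which patients reach TES or eTAU through the timing of a roll-out. There, group differences can be systematic and a propensity model has a job to do. Under patient-level randomisation, differences in baseline characteristics arise by chance, and three things follow.

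- **Model choice.** Whether the effectiveness model carries a propensity score is settled only after the arms have been compared, against a criterion nobody has written down.
- **Analysis set.** Trimming on a propensity score removes patients. If used, it excludes randomised participants and contradicts the SAP's own intention-to-treat sentence.
- **Covariate timing.** Only depression is labelled as baseline in the SAP's list. Protocol Table 1 collects other mental health treatment at weeks 0, 6 and 12, so a variable measured after randomisation could enter the score.

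Two analysts following the SAP faithfully could therefore fit different models to different patients from the same trial.

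**Working it through.** **1. The two texts side by side.**

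| Item | Protocol | SAP |
|---|---|---|
| Allocation | Patient-level randomisation | Not mentioned |
| Timing of roll-out | No delay described | Delay cited as a source of bias |
| Effectiveness model | GLMM, intention to treat | GLMM, intention to treat, propensity adjustment if groups differ |
| Exclusion by score | None | Optional, no rule |

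The nearest trace of a roll-out in the protocol is in Study Endpoints, which cites references 53-55 for the hybrid design. Two of those have stepped-wedge titles. That does not describe a delay in this trial.

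**2. How often chance alone would trigger the rule.** The plan gives no figure to reproduce, so these values are illustrative. Inputs: 85 patients (protocol), and 7 listed characteristics, or 8 if race and ethnicity are separated (SAP). Assumptions: independent characteristics, correct randomisation, and the thresholds shown.

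- Any p<0.05: 1 - 0.95^7 = 0.302; 1 - 0.95^8 = 0.337.
- Any standardised difference above 0.25: SE = sqrt(1/n1 + 1/n2). The chance per characteristic is 0.249 for 43/42 and 0.259 for 34/51. With 7 characteristics this gives 0.865-0.877; with 8, 0.899-0.909.
- Any standardised difference above 0.1: over 0.99.

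The range from 30% to over 99% comes almost entirely from a threshold that the SAP omits.

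**3. What trimming would remove.** In simulated null trials of 85 that triggered the rule, a common-support rule removed on average 6.4-9.4 patients, and a rule keeping scores from 0.1 to 0.9 removed 0.4-3.0. Losing 8 of 85 (42.5 per arm to 38.5) raises the detectable difference from 0.615 x 5 = 3.07 to 0.647 x 5 = 3.23 PHQ-9 points, which is 0.16 points.

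**4. What the rule does to the result.** Simulated null trials used 85 patients, splits 43/42 and 51/34, 7 normal baseline covariates and a fixed trigger (any p<0.05, or any standardised difference above 0.25). When triggered, the score was adjusted for, with and without common-support trimming. The outcome's correlation with one covariate was 0 or 0.5. Two-sided type I error was about 2.4-5.5%, and mean bias was zero within simulation error. The values below 5% arose where a prognostic covariate was otherwise left out.

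**5. Separate minor point: power** (two-sided 5% assumed, 80% power, SD 5, independent patients).

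- Protocol: "we provide an estimate of effect that we can detect with 100 randomized participants", effect size 0.58. Recomputed: 0.566 for 50/50 and 0.578 for 40/60, so 0.58 is reproduced with the unequal split.
- SAP: 30 eTAU and 45 TES, clinic ICC 0.01, effect size 0.76. Without clustering, 30/45 gives 0.669. The design effect needed is (0.76/0.669)^2 = 1.29 = 1 + (m - 1) x 0.01, so m is about 30 patients per clinic, which the SAP does not state.
- Planned 85: 0.615 for 42.5/42.5 and 0.628 for 34/51, or 3.07-3.14 PHQ-9 points.

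**The case against.** **No statistical harm under randomisation.** With a fixed threshold and baseline covariates, the rule leaves the estimate unbiased and does not inflate type I error, and the precision loss is small. This stands. A reader might infer that the planned analysis is biased or anti-conservative; the calculations do not support that. The result does assume a fixed threshold and covariates measured before randomisation, and the SAP guarantees neither.

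**Intention to treat is breached only conditionally.** The groups must differ and trimming must also be judged necessary. This stands too. Propensity adjustment alone keeps every randomised patient and does not conflict with intention to treat.

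**A delayed roll-out may have been run.** The SAP is the later document, so a reader might infer that the design changed or that patients were not randomised. Neither document says so, and the protocol states randomisation repeatedly. Equally, the documents cannot prove that the SAP wording is simply left over. They can only be said to conflict.

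**It is a pilot.** That lowers the stakes, but the SAP still specifies a comparative effectiveness analysis.

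**The clustering terms are not a fault.** Care-manager and clinic correlation is compatible with randomising patients.

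**The SAP's 75 is a floor.** It is labelled conservative, with more expected, and the protocol's 100 matches its own Enrollment Timeline. Both are fair. Nor is 0.76 shown to be an arithmetic error, since it is reproduced at about 30 patients per clinic. What remains is that neither figure is for 85.

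**Conclusion.** The plan is wrong as written and should be fixed, but this is not a fatal defect. The SAP's time-delay rationale contradicts the protocol's design. Its difference trigger and optional trimming leave the effectiveness model, and possibly the analysis set, open until the data have been seen. The size of the problem is undetermined discretion: across plausible thresholds, chance would trigger the rule in anything from about 30% to nearly all correctly randomised trials of 85. Beyond that, the cost is some lost precision (about 0.16 PHQ-9 points if 8 patients are trimmed) and sometimes conservative inference. These figures rest on assumed thresholds, trimming rules and independent characteristics. The finding itself rests on the text, and on the trial having been randomised as the protocol states. The mismatch in power sample sizes is separate and minor.

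**What to change.** Reconcile the SAP's Effectiveness and Power paragraphs with the protocol's Objectives, Study Endpoints and Data Analysis Plan.

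**If the trial was randomised as stated:**
- Delete the time-delay rationale, the difference trigger and the trimming.
- Analyse all randomised participants as randomised, with one prespecified covariate set, measured at baseline and applied unconditionally. Include baseline PHQ-9, and the antenatal/postpartum stratum if randomisation was stratified by it.
- Report group characteristics descriptively, and label any propensity analysis as a sensitivity analysis. Care-manager and clinic terms may stay.

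**If a delayed roll-out was actually run:** correct the protocol's design statement, and prespecify the threshold for a difference, the adjustment and the trimming rule.

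**Power:** give one figure in both documents for the actual sample size and allocation ratio, and state the patients per clinic if an ICC is used.

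For the randomised design the cost is SAP wording and one harmonised power paragraph, with no new data, visits or patients. The roll-out case also needs a corrected protocol design statement.
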